7.1 Institutional Review Board/Ethics Committee Approval

Prior to enrolling patients into the study, the investigator will ensure that proper IRB/EC approval is obtained in accordance with applicable local state and federal laws and regulations. The IRB/EC shall approve all study documents as appropriate, including but not limited to the final protocol, amendments to the protocol, Instructions for Use, and the Informed Consent Form.

The investigator will report to the Sponsor or designee immediately if, for any reason, the approval to conduct the investigation is withdrawn by the IRB/EC or Competent Authority. The report will include a complete description of the reason(s) for which approval was withdrawn.

7.2 Informed Consent

The investigator is responsible for ensuring that a signed and dated informed consent is obtained in accordance with Section 6.5 of this protocol and according to country and local requirements prior to conducting any study-related assessments, prior to administration of any pre-procedure medications or sedation, and prior to enrolment into the study.

7.3 Adherence to Protocol/Amendments and Applicable Law

The investigator is responsible for overseeing, ensuring that the study is conducted, and completing the study according to this protocol and in accordance with the relevant aspects of EN ISO 14155:2011, Declaration of Helsinki, along with any conditions imposed by the reviewing IRB or EC and all other applicable regulations. The investigator shall approve and adhere to this protocol and any amendments that arise during the course of the study.

It is the investigator's responsibility to ensure that the staff assisting with the study have the appropriate qualifications, are fully instructed on the study procedures, and will respect the confidentiality statement.

7.4 Case Report Form Completion

The investigator and study staff shall complete the case report forms (CRFs) associated with this study. Subject numbers shall be used to identify individual subjects in this study. The CRFs should be a complete and accurate record of subject data collected during the study according to relevant aspects of ISO 14155 and Good Clinical Practices (GCP) requirements. It is the investigator's responsibility to ensure the quality of the data collected and recorded.

7.5 Image Upload

Sites will be provided with instructions for how images should be collected and submitted within 14 days of the acquisition of the final required imaging at 72-hr post randomization (MM group) or 24-hr post Artemis (MIS group) visit. Additional images may be requested for adverse event adjudication. In the case of rebleeding immediate post procedure image may be requested for upload. If the site is unable to provide the images within this timeframe, the appropriate Sponsor contact should be notified. Study staff shall ensure that no images contain protected health information or personally identifying information as defined per local regulatory requirements.

7.6 Reporting

The investigator will be responsible for reporting the following:

7.6.1 Adverse Events

Adverse events or adverse device effects must be recorded by the investigator on the CRFs and must be carefully monitored during the study. All adverse events will be collected starting at enrollment through discharge and/or 7 day visit. After discharge and/or 7 day visit, all SAEs and neurological AEs are reportable through final follow-up visit.

Minimum requirements of data to be recorded are: type of event, duration of event (start through end), seriousness, action taken, outcome, and causality.

In order to ensure prompt reporting of AEs, we require that all reportable AEs (as well as all related study data) be entered timely into the Electronic Data Capturing (EDC) web-based database. All UADE should be reported immediately by calling Penumbra Clinical Affairs and all SAEs should be reported in the EDC within 72 hours of the study site staff first being made aware of the occurrence of the SAE. If the EDC system is unavailable, a written report can be sent via email to Penumbra.

The investigator must report the SAE or ADE to the IRB/EC according to local requirements. Reporting time frames should comply with local or national requirements. In addition, the investigator should report to the Sponsor and IRB/EC any device malfunctions that could have led to a SAE, if required by national regulations or by local authorities.

For the purpose of reporting within this protocol, pre-existing conditions or planned procedures for pre-existing conditions are not reported as AEs unless there is worsening of the condition with an increase in severity or frequency during the course of the investigation. An event does not need to be reported as a SAE if it represents a relapse or an expected change or progression of the condition. This type of event is considered an AE. All deaths should be reported regardless of causality. When reporting a death, the primary condition or

diagnosis that contributed to the fatal outcome should be reported as a SAE with an outcome of death. If the cause of death is unknown, please report “unknown cause of death” as an SAE.

Detailed form and narrative reports of the following specific adverse events will be obtained:

- Death (all cause) within 30 days of enrollment
- Death within 7 days of enrollment: Immediate periprocedural death
- Symptomatic Re-Hemorrhage or New Hemorrhagic Event: Any new intracranial hemorrhage or increase in size of pre-existing hemorrhage (IPH, IVH or extra-axial bleed) within 30 days associated with an NIHSS increase of ≥ 4 or a GCS decrease > 2 persisting for at least 24 hours, requiring emergency surgical decompression or resulting in death.
- Symptomatic Evolution of Perihematomal Edema: Edema with increased mass effect or uncontrolled ICPs within 30 days requiring emergency surgical decompression NOT related to new or increased hemorrhage (i.e. edema related) associated with an NIHSS increase of ≥ 4 or a GCS decrease > 2 persisting for at least 24 hours, requiring emergency surgical decompression or resulting in death.
- Symptomatic Ischemic Stroke: A new ischemic stroke (ipsilateral, contralateral; contiguous with bleed/operative site or remote; cortical, subcortical or perforator distribution) within 30 days associated with an NIHSS increase of ≥ 4 or a GCS decrease > 2 persisting for at least 24 hours, requiring emergency surgical decompression or resulting in death.
- Surgical complications related to MIS: Surgical site infection, brain abscess or confirmed meningitis, or documented complication(s) deemed specifically related to the procedural anesthetic (medication, access or intubation related) within 30 days.

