6.2 Study Visits

Subjects enrolled in this study will follow the visit schedule below and will continue to receive standard of care treatment at each follow up visit.

- Initial Screening/Baseline
- Final Screening
- Treatment Procedure (if randomized to MIS)
- Post procedure (within 24 (± 12) hours, MIS subjects) or 72 (± 24 , MM) hours after presentation
- 7 days post-enrollment or discharge (whichever comes first)
- Discharge (if beyond 7 days)
- 1 month (defined as 30 days) follow-up (± 14 days)
- 3 month (defined as 90 days) follow-up (± 14 days)

- 6 month (defined as 180 days) follow-up (\pm 21 days)
- 12 month (defined as 365 days) follow-up (\pm 35 days)

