6.9 Day 7/Discharge

The subject may be discharged from the hospital when clinically stable, at the Investigator's discretion. At day 7, the following will be completed by a qualified member of the research or clinical care team: a focused physical exam, a neurological exam (including GCS, NIHSS and mRS), a review of any adverse events, and a review of selected current medications. If discharge occurs before 7 days after randomization, the discharge clinical examinations will also substitute for the 7-day clinical evaluation and a standard of care CT (preferred) or MR will be obtained at that time. For subjects who remain in the hospital past Day 7, only SAEs and neurological AEs are reportable. For all subjects who expire prior to the Day 7/Discharge assessment, available information regarding the primary cause of death will be recorded, as well as whether the subject made "do not resuscitate" (DNR) prior to expiration.

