6.10.2 Unscheduled Visits

If a subject returns to the study site between follow-up visits a focused exam and mRS value should be obtained and recorded in the unscheduled visit CRF. Subject should also be screened for reportable adverse events and any medications used to treat those events, as well as any changes to medications should be recorded.

Table 2: Schedule of Assessments*

ACTIVITY	INITIAL SCREENING / BASELINE	FINAL SCREENING	TREATMENT PROCEDURE	MM ONLY: 72-HOUR POST RAND (±24 hours)	MIS ONLY: 24-HOUR POST ARTEMIS (±12 hours)	DISCHARGE AND /OR 7 DAYS (± 1 day)	30 DAY (± 14 days)	90 DAY PHONE CALL (± 14 days)	180 DAY (± 21 days)	365 DAY (± 35 days)	UN SCHEDULED
Informed Consent		X									
Verify I/E Criteria		X									
Medical History	X										
Focused Exam		X		X	X	X	X		X	X	X
Standard of Care Labs	X	X ²		X	X	X					
Pregnancy Test⁴		X									
CT/MR	X ¹	X ^{1,2,3}	X	X ¹	X ¹	X ²					
CTA or MRA	X	X ³									
Barthel Index		Historic					X	X	X	X	
NIHSS	X ²	X ⁶		X ⁶	X ⁶	X ⁶	X ⁶	X ^{2, 6}	X ⁶	X ⁶	X ²
GCS	X ²	X		X	X	X	X	X ²	X	X	X ²
mRS⁶		Historic		X	X	X	X	X	X ⁸	X	X
Randomization		X ⁷									
Artemis Procedure⁵			X								
Stroke Impact Scale (QoL)							X		X	X	
EQ-5D-5L QoL							X	X	X	X	
Con Medications	X	X	X	X	X	X	X	X	X	X	X
Adverse Events Review			X	X	X	X	X	X	X	X	X

¹ Image to be sent to central core lab within 14 days of 72-hr post randomization (MM group) or 24-hr post Artemis (MIS group) visit

² If done as standard of care

³ As necessary to demonstrate hemostasis

⁴ For Women of childbearing potential

⁵ Under general anesthesia within 72 hours of ictus if randomized to MIS group

⁶ Performed by certified assessor (or physician) delegated for task

⁷ After all eligibility criteria confirmed

⁸ Performed by blinded certified assessor (or physician) delegated for task

* Subjects in both MM and MIS group should follow medical management per AHA/ESO guidelines

7. Investigator Responsibilities

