11.2. Analysis of Adverse Events

Adverse events will be coded using the MedDRA dictionary. The number and percentage of subjects with AEs and SAEs will be summarized by body system and preferred term. Each subject will be counted only once within a category. The specific categories analyzed will be those that are reported by at least three (3) percent of the subjects. The Clinical Events Committee adjudicated data supersedes the investigator reported data in all analyses of adverse events.

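### The protocol does not fix one end date for collecting non-serious, non-neurological adverse events, and the date depends on discharge, so their crude percentages could differ between arms through length of stay alone

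*Protocol*

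**What the plan says.** Four places in the protocol bear on when full collection ends.

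- **7.6.1 (Adverse Events):** "All adverse events will be collected starting at enrollment through discharge and/or 7 day visit". The next sentence adds: "After discharge and/or 7 day visit, all SAEs and neurological AEs are reportable through final follow-up visit".
- **Table 2 (Schedule of Assessments):** a single column headed "DISCHARGE AND /OR 7 DAYS (± 1 day", with a closing bracket after the tolerance.
- **6.2 (Study Visits):** the visit is at "7 days post-enrollment or discharge (whichever comes first", and a separate later visit is listed as "Discharge (if beyond 7 days". These lines define visits and do not mention adverse event collection.
- **6.9 (Day 7/Discharge):** for inpatients, "For subjects who remain in the hospital past Day 7, only SAEs and neurological AEs are reportable". For earlier discharges, "If discharge occurs before 7 days after randomization, the discharge clinical examinations will also substitute for the 7-day clinical evaluation".

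After discharge, 6.10.1 directs sites to review records and question subjects about neurological and serious events only.

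On the analysis side, SAP 11.2 says: "The number and percentage of subjects with AEs and SAEs will be summarized by body system and preferred term". It limits the categories analyzed to those reported by at least 3% of subjects. It gives no onset window, no exposure adjustment and no split by collection period. Length of hospital stay is a secondary endpoint (Protocol 4.2.2) and one of the eight Bonferroni-adjusted analyses that SAP 10.4 allows for labeling claims.

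**The concern.** A crude percentage of subjects with an event compares two arms fairly only if both are watched for the same time. Here the watching time for one class of events ends at a date tied to discharge, and discharge timing may itself respond to treatment. If one arm goes home sooner, it has fewer days in which a non-serious pneumonia or urinary tract infection can be recorded, and it looks safer for that reason alone. The 3% threshold means the window can also decide which categories appear in the table.

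The unclear wording adds a second problem. A site with an inpatient who develops such an event on Day 10 could record it under one reading of 7.6.1 and leave it out under 6.9, so practice may vary between sites.

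**Working it through.** **Step 1. What each text implies for an event that is neither serious nor neurological.**

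| Subject | 7.6.1 and Table 2 | 6.2 with 6.9 |
|---|---|---|
| Discharged Day 4, event on Day 6 | Unclear: collected if the later date governs | Not collected: the discharge examination replaces the Day 7 evaluation, and later contacts ask only about neurological and serious events |
| Inpatient, event on Day 10, discharged Day 14 | Unclear: collected if the later date governs | Not collected: 6.9 says so directly |

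No single sentence states the earlier-of-two rule for adverse events. It is inferred from a visit definition (6.2), an explicit rule for inpatients (6.9) and the substitution of the discharge examination (6.9). Neither column gives every subject the same window.

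**Step 2. Size under the earlier-of-two reading.** The plan gives no adverse event rate or length-of-stay figure, so there is nothing of its own to reproduce. What follows is an illustration on assumed inputs.

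Assume the same constant daily hazard *h* in both arms. A subject observed for *w* days has at least one such event with probability P = 1 − exp(−*h* × *w*), where *w* = min(discharge day, 7).

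At *h* = 0.05 per day:
- discharge on Day 3: 1 − exp(−0.15) = 13.9%
- discharge on Day 5: 1 − exp(−0.25) = 22.1%
- seven full days: 1 − exp(−0.35) = 29.5%

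If 20% of one arm and 10% of the other leave on Day 5, and everyone else is observed for seven days, the spurious difference is (0.20 − 0.10) × (29.5 − 22.1) = 0.7 points. If 30% and 10% leave on Day 3, it is 0.20 × (29.5 − 13.9) = 3.1 points. At *h* = 0.2 with the same Day 3 discharges, it is 0.20 × (exp(−0.6) − exp(−1.4)) = 0.20 × (0.549 − 0.247) = 6.0 points.

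**Step 3. The same with a spread of stays.** Length of stay was simulated as lognormal with an SD of log stay of 0.7, and P was averaged over subjects. Medians, SD and hazards are all assumptions.

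| Median stay, days | Discharged before Day 7 | *h* = 0.02 | *h* = 0.05 | *h* = 0.10 |
|---|---|---|---|---|
| 14 v 14 | 16% v 16% | 0 | 0 | 0 |
| 14 v 21 | 16% v 6% | 0.4 | 0.8 | 1.3 |
| 10 v 14 | 31% v 16% | 0.7 | 1.4 | 2.2 |
| 7 v 14 | 50% v 16% | 1.8 | 4.0 | 6.2 |
| 5 v 10 | 69% v 31% | 2.7 | 5.8 | 9.1 |

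Entries are spurious differences in percentage points, and the arm with the shorter stay always has the lower percentage. With unequal stays the range is 0.4 to 9.1 points. The upper end needs most of one arm to leave before Day 7.

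**Step 4. With a fixed seven-day window and complete capture.** Both arms show 13.1%, 29.5% and 50.3% at the three hazards, so the difference is 0 in every scenario.

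**The case against.** The strongest reply is that little of clinical weight is exposed.

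- Serious and neurological events are collected to the final visit in every subject.
- The events singled out for narratives and DSMB review (7.6.1 and 12.2), including re-hemorrhage and surgical site infection, carry fixed windows counted from enrollment or stated as 30 days.
- Primary safety is 30-day mortality.
- SAP 11.2 summarizes and names no test, and SAP 11.3 makes these comparisons secondary and bars them from labeling.
- A Day 7 cut-off also fits 7.6.1.3, which does not expect events more than 7 days after the procedure to be related to it.

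All of this stands. It confines the point to non-serious, non-neurological events and to the any-event total, which changes only for subjects with no serious or neurological event.

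A reader might infer a much larger bias from the wording of 7.6.1. If collection ran to discharge, or to the later of the two dates, the Step 3 inputs with unequal stays would give 6.6 to 20.5 and 5.9 to 15.1 points respectively. The documents do not support relying on these figures, because 6.9 explicitly ends full reporting at Day 7 for inpatients. They show only what is at risk if sites follow 7.6.1 instead.

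A reader might also infer that the protocol expects the device to shorten stay and that the bias therefore favors it. Section 1.3.1 reports a shorter stay in an earlier trial of catheter drainage with tPA, which is a different technique. Listing stay as an endpoint is not a stated expectation, so no direction can be assumed.

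Finally, the constant hazard treats subjects fit for early discharge like those still in hospital, which probably overstates the events missed.

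**Conclusion.** The point holds as a risk limited to one class of events. The four protocol passages leave the end of full collection unresolved. Under either reading that end depends on the discharge date, and the SAP does not standardize for it. The earlier-of-two reading is the better supported one. Under it, the artefact is about 0.4 to 9 points if stays differ, for assumed hazards of 0.02 to 0.10 per day and the assumed stays above, and zero if stays are equal.

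It would go too far to say that adverse event percentages in general are not comparable between arms. Serious events, neurological events and 30-day mortality are untouched, and the documents contain no data showing that stays will differ.

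**What to change.** **Protocol 6.2, 6.9, 7.6.1 and Table 2:** state one rule, that all adverse events with onset from randomization (Day 0) through Day 7 are collected in every subject, whether or not discharged. Define the window by onset date, so that the one-day visit tolerance in Table 2 does not move it. For subjects discharged before Day 7, capture the remaining days at the Day 30 contact and record review already scheduled, and widen the 6.10.1 questions for that purpose.

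**SAP 11.2:** limit the all-event table to onset on or before Day 7, and report serious and neurological events separately over full follow-up.

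**Cost:** wording changes in both documents and a small amount of retrospective collection at Day 30. Recall and record review after early discharge are less complete than inpatient observation, so some dependence on discharge will remain. The zero in Step 4 assumes complete capture. The report should state this limitation.

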6.10.1 Post Discharge Assessments

- Focused Exam, which includes a review of subject's vitals.
- mRS: As described in section 6.4 above. It is preferred that mRS measurements are done at the study site, but if subject is unable to come into the study site for the follow-up visit, a mRS evaluation may be obtained via telephone for 30 day, 90 day, and 365 day using the approved telephone questionnaire/worksheet. The 180 day evaluation of mRS must be conducted in-person.
- Barthel Index: As described in section 6.4 above.
- NIHSS: As described in section 6.4 above.
- GCS: As described in section 6.4 above.

- EQ-5D-5L is a standardized instrument for use as a measure of health outcome. Applicable to a wide range of health conditions and treatments, the questionnaire provides a simple descriptive profile and a single index value for health status. The 90 day EQ-5D-5L should be done using the approved telephone questionnaire if the visit is conducted via the telephone.
- Stroke Impact Scale: Additionally, a quality of life scale outcome measure will be utilized in this study. Quality of life scales are designed to be sensitive to changes in outcome from mild and moderate stroke undetected by other outcome measures. Important parameters not fully interrogated by conventional outcome scales can be assessed by quality of life scales, including emotion, communication, cognition, and social role function. Standard measures, such as the mRS, primarily evaluate physical aspects of stroke outcome, not addressing more relevant quality of life measures. The Stroke Impact Scale is a validated assessment of quality of life specifically in patients with stroke.⁶³

All day 30, day 90, day 180, and day 365 outcome measures will be assessed by a qualified member of the research or clinical team. The schedule of neurological assessments is listed in Table 2. At each visit, the subject medical record will be surveyed for any new or interim neurological adverse or serious adverse events and selected concomitant medication. In addition, the subject, LAR, or approved delegate will be asked about any interim neurological adverse or serious adverse events. The subject, LAR, or approved delegate will also be specifically asked about any interim neurosurgical procedures. Best medical management should be followed throughout the post discharge follow up period.

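### Routine adverse event reporting narrows at Day 7 or discharge, but the listed surgical-complication event runs to Day 30 whatever its seriousness, and the protocol does not say which rule governs

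*Protocol*

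**What the plan says.** **General reporting rule.** Section 7.6.1 opens with full collection: "All adverse events will be collected starting at enrollment through discharge and/or 7 day visit". It then narrows: "After discharge and/or 7 day visit, all SAEs and neurological AEs are reportable through final follow-up visit". Section 6.9 applies the same limit to inpatients: "For subjects who remain in the hospital past Day 7, only SAEs and neurological AEs are reportable". Section 6.10.1 sets the follow-up survey to match: "At each visit, the subject medical record will be surveyed for any new or interim neurological adverse or serious adverse events". The subject or representative is asked about the same two classes of event, and about interim neurosurgical procedures.

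**Specific-event rule.** Later in section 7.6.1: "Detailed form and narrative reports of the following specific adverse events will be obtained". One entry on that list is "Surgical complications related to MIS: Surgical site infection, brain abscess or confirmed meningitis, or documented complication(s) deemed specifically related to the procedural anesthetic", with a 30-day limit and no seriousness criterion. Section 12.2 repeats the list as endpoints that the medical monitor assesses and presents to the DSMB.

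**Relatedness.** Section 7.6.1.3 says that events more than 7 days after the MIS procedure are not expected to be attributed to it.

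**Promised use.** Section 10.1 says that the treatment arm will give a prospective, independently adjudicated account of complication rates with the Artemis procedure.

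**The concern.** A superficial wound infection on Day 14 that needs no admission is neither serious nor neurological. It meets the listed definition, which runs to Day 30, but it falls outside what a site is told to report after Day 7 or discharge. A site could comply with one rule and breach the other, and nothing in the protocol ranks them.

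At stake is the surgical-complication rate in the only arm that has surgery. If sites work from the general rule, the rate that reaches the DSMB and the final report would be too low, and the error would favour the device.

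**Working it through.** The plan states no figure for this event, so the check compares the texts and then counts days.

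**1. Is the late event inside each rule?** Take a non-serious, non-neurological surgical site infection after Day 7 and by Day 30.

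| Text | Is the event covered? |
|---|---|
| 7.6.1, general rule | No: only SAEs and neurological AEs |
| 6.9, still in hospital | No: same limit |
| 6.10.1, follow-up survey | Not asked for |
| 6.10.2, unscheduled visits | Only if reportable, which refers back to 7.6.1 |
| 7.6.1, specific-event list | Yes: within 30 days, any seriousness |
| 12.2, DSMB endpoints | Yes: same definition |

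A non-serious, non-neurological anesthetic complication in the same period is in the same position.

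**2. Does the specific rule have its own route into the data?** Only in part. Section 7.6.1 says that the narrative reports will be obtained, but section 7.6.1.1 has the medical monitor review these categories as they are reported. That review depends on the site having recognised and entered the event. The site's instructions for looking (6.10.1) and for entering data (7.6.1, which refers to reportable AEs) both follow the general rule.

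**3. Length of the gap.** Day 0 is randomization (6.6). I count the 30 days from there too, because the surgical-complication entry does not name its starting point.

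- Closing at Day 7: 30 − 7 = 23 days, and 23 / 30 = 77% of the event window.
- With the ± 1 day on that visit (Table 2): 30 − 8 = 22 to 30 − 6 = 24 days.
- With earlier discharge, for illustration on Day 3: 30 − 3 = 27 days.

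Surgery follows randomization and must fall within 72 hours of ictus, so it comes less than 3 days after Day 0. Full AE collection after surgery then covers about 7 − 3 = 4 to 7 days, or fewer after early discharge.

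**4. What remains covered.** An infection that leads to admission or a longer stay meets the SAE definition in 7.6.1.2 and stays reportable to the end of follow-up. Brain abscess and meningitis would be expected to count as serious or neurological. The exposed events are the non-serious, non-neurological ones.

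**5. Attribution.** The listed event must be related to MIS. Under 7.6.1.3 an infection starting more than 7 days after surgery is not expected to be called procedure-related. Even a reported late infection could therefore be left out of the count.

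**The case against.** The strongest reply is that the specific instruction adds to the general one. Section 7.6.1 says outright that detailed reports of the listed events will be obtained, with a 30-day limit and no seriousness threshold. There are other routes as well. Section 3 says that participants will be routinely questioned about adverse events at visits. Table 2 schedules a focused exam and an adverse event review at Day 30. The question about neurosurgical procedures would bring out a wound revision. The DSMB and CEC charters, which are not among the documents, may set out how the listed events are captured.

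Much of this stands. A reader might infer that late non-serious wound infections are never collected. The documents do not support that: one rule asks for them and another leaves them out. What survives is that the visit-level survey in 6.10.1 does not prompt for them, and no text says which rule prevails.

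A reader might also infer that the cut-off itself is inconsistent, because 7.6.1 joins discharge and the 7-day visit loosely while 6.9 names Day 7. Section 6.2 defines that visit as the earlier of the two, and 6.9 lets an earlier discharge examination stand in for it. Read together, these largely settle the matter. The shorter window after early discharge is then a design choice.

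Finally, this event has no counterpart in the MM arm, so its undercount biases no between-arm test. Under SAP section 11.3, secondary safety comparisons are not used for labeling claims. Both points are correct and limit the consequence.

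**Conclusion.** The protocol contradicts itself on late surgical complications, and the passages must be reconciled. Sites following the general rule may not report non-serious, non-neurological surgical site infections or anesthetic complications in about 23 of the 30 days that the event definition covers. The MIS complication rate seen by the DSMB and promised in section 10.1 could then be too low.

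The number of events affected cannot be computed. One might multiply an assumed share of infections arising late by an assumed share that are non-serious: 50% to 75% for each gives 0.5 × 0.5 = 25% to 0.75 × 0.75 = 56% missed. Neither share is in the documents, and the product also supposes that every site ignores the narrative requirement. It does not measure the undercount.

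The conclusion assumes that at least some sites take the general rule as governing and that no unseen charter or CRF guideline overrides it. The primary safety endpoint is unaffected, because all deaths are reportable regardless of cause, and so is the primary analysis of the 180-day mRS. The clarification should be made, but it does not touch the trial's main inference.

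**What to change.** 1. In sections 6.9, 6.10.1 and 7.6.1, state that every event on the 7.6.1 specific-event list is reportable through Day 30 whatever its seriousness, and that sites ask about these events at the Day 30 visit. That visit already exists. Its ± 14 day window lets it fall as early as Day 30 − 14 = 16, so where it is held early the Day 90 contact should cover the remaining days.
2. Reconcile the 7-day convention in 7.6.1.3 with the 30-day definition in 7.6.1 and 12.2, so that a late infection, once reported, is not left out by default.

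The collection window for all other adverse events can stay as it is. Extending it to Day 7 for subjects already discharged would need an extra contact, or recall at Day 30, and the contradiction can be removed without it.

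The cost is protocol and CRF-guideline wording, a few more non-serious events to enter, and possibly a slightly less favourable MIS complication rate. No visit is added and treatment does not change.
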